### **Treatment group stopping rules**

If four or more subjects in a treatment group experience a treatment related grade 3 suspected adverse reaction (SAR) or laboratory abnormality, or one or more subjects in a treatment group experience a treatment related grade 4 SAR or laboratory abnormality, the study will be suspended pending an unblinded safety review of those subjects by the DSMB. This safety review might lead to the recommendation to discontinue a treatment group.

In case a treatment group has to discontinue the clinical study prematurely for any reason, the concerned subjects should be asked to perform an early termination visit. Additionally, women of childbearing potential will be followed up by a phone call, 3 months after the last vaccination to ensure no pregnancy occurred within this period as confirmed by a urine pregnancy test provided by the investigator.

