### 13.2 Safety Analysis

Solicited AEs (reactogenicity): Solicited local and solicited systemic AEs will be summarized for the 7 day period, by AE grade (mild, moderate, severe), by group and by dose. Solicited AEs will not be coded into MedDRA or assessed for relatedness. The number and percentage of subjects with AEs will be presented. Subjects who reported data for a solicited event at any time point during the time period summarized would be included in the denominator for that event. Thus, denominators for each solicited event will not include subjects who were missing all data for that event, during the time period summarized. P-values for AE rates for MV-CHIK vs. Priorix® (or equal control-vaccine), for the same schedule, will be provided in summary tables (pairwise comparisons).

Unsolicited AEs: Separately, the number and percentage of subjects with unsolicited treatment emergent adverse events (TEAEs), medically-attended AEs (MAEs) and serious adverse events (SAEs) will be presented for each treatment group overall and by system organ class/preferred term, and by AE grade, and relatedness. All SAEs and MAEs are also included in TEAE tables. Arthritis AEs, AEs of special interest (AESI), will be included in the TEAE tables. For unsolicited AEs, all subjects entered into the study who receive at least one vaccination will be included in the safety analysis based on the product received (“as treated”), for the time period summarized. P-values for AE rates for MV-CHIK vs. Priorix®, for the same schedule, will be provided in summary tables (pairwise comparisons).

Unsolicited AEs and concomitant diseases will be coded using the MedDRA coding dictionary; concomitant medications will be coded using the WHO Drug Dictionary.

Solicited and unsolicited AEs (local and systemic), MAE, SAE and AESI (arthralgia) will be recorded up to Visit 6 (day 224).

Safety analyses will be performed by means of descriptive measures. Laboratory values will be assigned a grade. Changes in laboratory values and grades as well as vital signs from study entry to end of treatment/follow up will be analyzed descriptively.

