The statistical analysis plan is based on the final study protocols for Austria (Version 1.5; 24-Nov-2016) and Germany (Version 1.6; 19-Apr-2017). No changes in the conduct of the planned analysis as described in the CSP are intended.

However, the time point of the Preliminary Analysis was moved forward to August 2017. The Preliminary Analysis was initially planned to take place after all subjects completed Visit 3.

Page 21 of 47

3. **OVERALL STUDY INFORMATION**

Treatment groups for the preliminary analysis as well the final analysis are defined in section 2.3. Overall study information analysis will be prepared for the:

- Preliminary analysis: mITT population. •
- Final analysis: Safety, mITT and PP population. •

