8.3 Adverse Events

Adverse Events are statistically analyzed once for the Preliminary Analysis up to Visit 3 and once for the final analysis.

The Preliminary Analysis includes all Adverse Events with a start date which is at of before the date of Visit 3. Adverse Events will be coded using the Medical Dictionary for Regulatory Activities (cp. section 2.15)

Solicited AEs comprise reactions at the injection site or systemic reactions that are typical for vaccinations:

- Solicited local AEs (injection site reactions) are the following: injection site pain, tenderness, pruritus, erythema (redness), edema, induration (hardening)
- Solicited systemic AEs are the following: headache, fever, myalgia, limb discomfort, arthralgia, flu-like symptoms, nausea, vomiting, rash and excessive fatigue.

For solicited local and systemic AEs were summarized for a 7 day period. Solicited AEs will not be coded into MedDRA and no assessment of relatedness was performed.

An AE is considered to be related to study drug if the "Causal relationship to study treatment" was considered "definite", "probable", "possible" or the classification is missing.

For solicited local and systemic AEs the following tables will be tabulated:

- at least one AE
- at least one serious AE
- at least one severe AE

SAP (MV-CHIK-202, FINAL 3.0, 09-May-2018) Page 32 of 47 Based on: STAT03_A Statistical Analysis Plan Version 5.0, Effective Date 16-Dec-2016 Confidential and intellectual property of Assign DMB. No part of this document or its contents may be duplicated, referenced, published or otherwise disclosed in any form or by any means without prior written consent of Assign DMB.

• at least one AE by severity

An AE is considered to be a treatment-emergent AE (TEAE) if, and only if, first onset or worsening is simultaneous with or after first vaccination (AE start date is greater or equal first vaccination date). AEs for which it cannot be clearly decided if the start date was before or on/after first vaccination will be considered treatment-emergent, following a worst case approach.

For unsolicited AEs the following tables will be tabulated:

- at least one TEAE
- at least one severe TEAE
- at least one serious TEAE
- at least one TEAE related to study drug
- at least one medically attended TEAE
- at least one TEAE where an action was taken (i.e. no action taken was NOT ticked)
- at least one TEAE of special interest (arthritis)

The same tables grouped by SOC and PT will be provided.

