Statistical analysis will be performed as described in section 2.7.3.

The following further summary tables will be provided:

- Number of subjects with solicited adverse event by symptom and severity -- MV-CHIK vs. control
- Number of subjects with unsolicited adverse event by symptom and severity -- MV-CHIK vs. control, for the five most frequent adverse events

The following listings will be provided:

- All AEs (including information if local/ systemic solicited, unsolicited)
- Solicited local adverse events
- Systemic adverse events
- Unsolicited adverse events
- Serious adverse events (SAEs)
- AEs leading to death

The following figures will be provided:

- Bar chart for number of subjects with solicited adverse event by event and maximum severity
- Bar chart for number of subjects with unsolicited adverse event by preferred term and maximum severity, where only the five most frequent terms will be included

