			overall (mITT population)		
T-cell Ar	nalysi	S			
3.1.20	Х	Х	Number of subjects of functional Chikungunya virus specific T cells		
			by visit, treatment group and overall (mITT population)		
3.1.21	Х	Х	GMT for T cell immune by visit, treatment group and overall (mITT		
			population)		
3.1.22	х	Х	ANOVA with fixed factor treatment group for T-cells by visit (mITT		
			population)		
Measle	s Viru	s Sh	edding		
3.1.23		х	Number of subjects participating in measles virus shedding by		
			treatment group and overall (mITT population)		
3.1.24		х	Number of sample performed by visit, treatment group and overall		
			(mITT population)		

Based on: STAT03_A Statistical Analysis Plan

Version 5.0, Effective Date 16-Dec-2016

Confidential and intellectual property of Assign DMB. No part of this document or its contents may be duplicated, referenced, published or otherwise disclosed in any form or by any means without prior written consent of Assign DMB.

3.1.25		Х	Number of subjects with positive shedding results in urine by visit,	
			treatment group and overall (mITT population)	
3.1.26		Х	Number of subjects with positive shedding results in saliva by visit,	
			treatment group and overall (mITT population)	
3.2.1 -		х	Repeat the tables for the PP population	
3.2.26				
			Safety Analysis	
4.1		Х	Extent of Exposure (Safety population)	Study duration,
				Treatment duration
4.2	Х	х	Solicited Adverse Events ('Analysis' population)	AE, serious AE, severe AE, AE by severity
4.3	x	x	Unsolicited Adverse Events ('Analysis' population)	TEAE, serious TEAE, severe TEAE, TEAE related to study drug, medically attended TEAE, TEAE where an action was taken, TEAE of special interest (arthritis)
4.4	х	х	At least one unsolicited TEAE by SOC, PT, treatment group ('Analysis' population)	
4.5	х	х	At least one severe unsolicited TEAE by SOC, PT, treatment group ('Analysis' population)	
4.6	Х	х	At least one serious unsolicited TEAE by SOC, PT, treatment group ('Analysis' population)	
4.7	Х	х	At least one unsolicited TEAE related to study drug by SOC, PT, treatment group ('Analysis' population)	
4.8	х	х	At least one medically attended unsolicited TEAE by SOC, PT, treatment group ('Analysis' population)	
4.9	х	х	At least one unsolicited TEAE where an action was taken SOC, PT, treatment group ('Analysis' population)	
4.10	х	х	At least one unsolicited TEAE of special interest by SOC, PT, treatment group ('Analysis' population)	

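### The protocol promises unsolicited adverse events by grade for each treatment group, but the SAP tables single out only severe events, so mild and moderate are never separated by group

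*SAP*

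**What the plan says.** Protocol 13.2 states that the number and percentage of subjects with unsolicited TEAEs, medically attended events and serious events "will be presented for each treatment group overall and by system organ class/preferred term, and by AE grade, and relatedness". The statistical methods paragraph of the synopsis says much the same.

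SAP 8.3 lists seven tabulations for unsolicited events, and SAP 10.1 gives the same seven as the content of Table 4.3: "TEAE, serious TEAE, severe TEAE, TEAE related to study drug, medically attended TEAE, TEAE where an action was taken, TEAE of special interest (arthritis". For the class and term level, SAP 8.3 adds: "The same tables grouped by SOC and PT will be provided". These are Tables 4.4 to 4.10, of which only Table 4.5 (severe events) concerns severity.

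For solicited events, Table 4.2 has the content "AE, serious AE, severe AE, AE by severity", which includes a full severity breakdown.

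One further summary of unsolicited events is by severity: "Number of subjects with unsolicited adverse event by symptom and severity -- MV-CHIK vs. control, for the five most frequent adverse events". Figure 4.3 is a bar chart of the same content.

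On departures from the protocol, SAP 2.17 says: "No changes in the conduct of the planned analysis as described in the CSP are intended".

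**The concern.** The protocol names both the breakdown (grade) and the level (each treatment group, overall and by class and term). The SAP fixes the table set, and the breakdown is missing from it. Table 4.2 has a by-severity row and Table 4.3 does not, which looks more like an oversight than a decision. Because SAP 2.17 reports no change, a reader of the study report would not learn that a promised presentation was left out.

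Identifying a dose and schedule for Phase 3 is a secondary objective (Protocol 3.2), alongside safety and tolerability. If unsolicited events moved from mild to moderate with the higher dose or with one schedule, no planned table would show it by group.

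**Working it through.** The point concerns which tabulations exist. The plan gives no figure to reproduce, so the check is a comparison of outputs.

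| Source | By treatment group | Coverage of unsolicited events | Mild and moderate separated |
|---|---|---|---|
| Protocol 13.2 (commitment) | Yes | All, overall and by class/term | Yes (by grade) |
| SAP Table 4.3 | Yes | All, overall | No, severe only |
| SAP Tables 4.4–4.10 | Yes | All, by class/term | No, severe only (Table 4.5) |
| SAP Table 4.11 | End of legend lost | Related events only, by class/term | Cannot be read |
| SAP 8.3 further summary and Figure 4.3 | No, MV-CHIK versus control | Five commonest terms | Yes |
| SAP Tables 4.32–4.35 and 4.41–4.44 | Yes | None (diary symptoms) | Yes |
| SAP Listings 4.9/4.10 | Group shown for each event | All, event by event | Shown, but no counts |

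No legible row after the first has all three properties. Relatedness, the other half of the protocol's phrase, is covered by Tables 4.3 and 4.7.

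**What the Table 4.3 rows leave unsplit.** Inputs are the Phase 1 results in Protocol 2.4: 42 subjects, 28 with any unsolicited event, 2 with a severe one, 5 with a related one.
- The stated percentages reproduce: 28/42 = 66.7%, 2/42 = 4.8%, 5/42 = 11.9%.
- Subjects with events but no severe event: 28 − 2 = 26. With the Table 4.3 rows alone, these 26 form one mild-or-moderate remainder.

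**Severity within related events.** Let s be the number of subjects with a severe event, r the number with a related event and n the group size. If only s and r are tabulated, the number of subjects with both lies between max(0, s + r − n) and min(s, r).
- Phase 1 (s = 2, r = 5, n = 42): max(0, −35) = 0 to min(2, 5) = 2.
- Assumed group of 60 with s = 4 and r = 7: max(0, −49) = 0 to min(4, 7) = 4.

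Separate severe and related rows therefore do not give the combination. This supports an optional addition; it does not show a broken commitment.

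**Scale.** Protocol 14.2 defines mild, moderate and severe. Protocol Table 9 has a fourth grade, including for general illness or clinical adverse events. A single severe row does not say whether grade 4 is inside it. SAP 2.11 imputes missing severity as severe and calls this the worst case, which fits a three-level scale only.

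**The case against.** The strongest reply is that little is lost. Severe, serious, related and medically attended unsolicited events are all tabulated by group, class and term. The severity of solicited reactions is shown by group in Table 4.2 and the diary tables. Listings 4.9/4.10 give group, severity and causality for every unsolicited event, so the missing counts could be made by hand. This limits the importance of the gap but does not close it: the protocol promised numbers and percentages per group, and a listing is not that.

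Four stronger readings are tempting, and the documents do not support them.

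- *The tables omit the quantity on which the stopping rules rest.* The group rule begins "If four or more subjects in a treatment group experience a treatment related grade 3 suspected adverse reaction (SAR) or laboratory abnormality". It also covers laboratory abnormalities and is not confined to unsolicited events. Protocol 11.1 gives the DSMB the task of determining during the study, on unblinded data, whether stopping rules are met. A table of unsolicited events would not show how near a group came to its limit.
- *Related grade 3 or 4 events go uncounted.* They appear in the listings. The legible part of the Table 4.11 legend matches that of Table 4.7, but its end is lost in the text available, so a severity split there cannot be ruled out. Table 4.11 could not supply the split for all TEAEs, because its legend is limited to related ones.
- *The protocol promises grade crossed with relatedness.* Its wording is met by two separate presentations.
- *Nearly all the information is lost, judging by the share of Phase 1 events that were not severe.* The planned tables count subjects, not events, and Phase 1 reports no split between mild and moderate, so such a share does not measure what is lost.

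**Conclusion.** The point holds in a narrow form. The SAP leaves out, without saying so, a by-grade presentation of unsolicited TEAEs per treatment group that the protocol commits to. The one severity summary it does plan covers five terms and cannot compare doses or schedules.

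The weight is low. The gap concerns how safety data are presented; it does not touch the immunogenicity analysis, and the underlying data are collected and listed. The Phase 1 figure of 26 of 28 subjects illustrates how much could sit in the undivided category. It comes from a small trial with different doses and cannot predict this one.

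The conclusion assumes that the legible table list is complete apart from the end of the Table 4.11 legend.

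**What to change.** 1. Add a row block to Table 4.3 for TEAEs by maximum severity, as Table 4.2 already does for solicited events.
2. Give Table 4.4 by class, term and maximum severity for each treatment group.
3. State how grade 4 in Protocol Table 9 maps to the mild, moderate and severe categories of Protocol 14.2, and align the worst-case imputation in SAP 2.11 with that mapping.
4. Optional, and not promised by the protocol: related TEAEs by maximum severity for each group, unless Table 4.11 already gives this.

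If the sponsor prefers the present table set, SAP 2.17 should declare and explain the departure.

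The cost is a few rows and one or two longer tables, programmed from severity and causality fields that the listings already use. The only downside is a slightly longer table set.

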10.2 List of Data Listings

No	IA	FA	Legend	Content
			Overall Study Information	
1.1	x	x	Analysis population details	Subject number, Country, Site, Treatment group, Safety population, Reason for not Safety, mITT population, Reason for not mITT, PP population, Reason for not PP
1.2	х	х	Screening failures with reason	Subject number, Country, Date of informed consent, Reason for screening failure
1.3		х	Protocol deviations	Subject number, Country, Treatment group, Deviation type, Deviation, Severity
1.4	x	х	Early terminations with reason (Randomized subjects)	Subject number, Country, Treatment group, Date of study end, Reason, Visit attendance status
1.5	х	х	Attended visits (Randomized subjects)	Subject number, Country, Treatment group, Visit, Date of Visit, Reason if out of time window
			Baseline Data	
2.1	х	х	Demographic data (Randomized subjects)	Subject number, Country, Treatment group, Year of birth, Date of IC, Age [years], Gender, Ethnic origin, Other origin
2.2	x	х	Physical examination (Randomized subjects)	Subject number, Country, Treatment group, Body system, Specification other body system, Result, Specification of Abnormality
2.3	х	x	Vital signs (Randomized subjects)	Subject number, Country, Treatment group, Systolic blood pressure [mmHg], Diastolic blood pressure [mmHg], Pulse rate [b/min], Body temperature [°C]
2.4	х	х	Virology (Randomized subjects)	Subject number, Country, Treatment group, Date of sample drawn, Parameter, Result
2.5	x	х	Pregnancy test (Randomized subjects)	Subject number, Country, Treatment group, Urine pregnancy test performed, Date of of pregnancy test, Result
2.6	х	х	Medical history (Randomized subjects)	Subject number, Country, Treatment group, Condition, MedDRA Preferred Term, System organ class, Start date, End date, Ongoing
2.7	x	x	Vaccination history (Randomized subjects)	Subject, Treatment group, Date of last measles vaccination, Any vaccinations within 3 years prior screening, Date of vaccination, Trade name
2.8	х	X	Prior medications (Randomized subjects)	Subject number, Country, Treatment group, Medication, ATC (level 2), Start date, End date, Dose frequency, Route of administration, Indication
2.9	X	x	Concomitant medications (Randomized subjects)	Subject number, Country, Treatment group, Medication, ATC (level 2), Start date, End date, Ongoing, Dose frequency, Route of administration, Indication

Confidential and intellectual property of Assign DMB. No part of this document or its contents may be duplicated, referenced, published or otherwise disclosed in any form or by any means without prior written consent of Assign DMB.

			Immunogenicity Analysis	
3.1	х	х	Functional Antibodies Assessment (PRNT)	Subject number, Country, Treatment group,
			(Randomized subjects)	Visit, Functional antibody titer sample drawn,
				Date of sample, Time of sample, Titer [IU/ml]
3.2	Х	х	Functional Antibodies Assessment (ELISA)	Subject number, Country, Treatment group,
			(Randomized subjects)	Visit, Functional antibody titer sample drawn,
				Date of sample, Time of sample, Titer [IU/ml]
3.3	Х	х	Measles Antibodies Assessment (Randomized	Subject number, Country, Treatment group,
			subjects)	Visit, Measles antibody titer sample drawn,
				Date of sample, Time of sample, Titer [IU/mI],
				negative (no quantit. result available), Reason
				not drawn
3.4	Х	х	T-cell details (Randomized subjects)	Subject number, Country, Treatment group,
				Visit, Functional antibody titer sample drawn,
				Date of sample, Time of sample, Number of
				spots
3.5		х	Measles Virus shedding (Randomized subjects)	Subject number, Country, Treatment group,
				Measles virus shedding observation, Date of
				separate IC, Visit/Day, Date, Urine sample
				obtained, Saliva sample obtained, Whole Blood
				sample obtained, urine result, saliva result,
			Safety Analysis	
4.1		х	Extent of exposure (Randomized subjects)	Subject number, Treatment group, Date
				informed consent, Date of first vaccination,
				Date of last vaccination, Date of last attended
				visit, Treatment duration [days], Study duration
				[days]
4.2		х	Study medication details (Randomized subjects)	Subject number, Country, Treatment group,
				Vaccination been performed, Date/time,
				Nedication, Reason not vaccinated
1.0	Х	х	Adverse Events (Randomized Subjects)	Subject number, Treatment group, AE term,
4.3				Part 1: Country, Type (local solicited, systemic
				Solicited, unsolicited), MedDRA Preferred Term,
				Medically attended
1 1				Dert 2: Severity Serieue AF Coupelity Action
4.4				taken in general Action taken on the
				investigational product. Outcome
	v	v	Solicited local AFs (Bandomized subjects)	Subject number, Country, Treatment group, AF
	^	^		term
45				Part 1: Start date End date Medically
				attended Severity Serious AF
46				Part 2: Causality Action taken in general Action
				taken on the investigational product. Outcome
-	x	x	Systemic AFs (Randomized subjects)	Subject number Country Treatment group AF
	Â	^		term
4.7				Part 1: Start date, End date, Medically
				attended, Severity, Serious AE
4.8				Part 2: Causality, Action taken in general. Action
				taken on the investigational product. Outcome
	х	х	Unsolicited AEs (Randomized subjects)	Subject number. Treatment group. AE term.
4.9		1		Part 1: Country, MedDRA Preferred Term
				System organ class, Start date. End date.
				Medically attended
4.10		1		Part 2: Severity, Serious AE, Causality. Action
-		1		taken in general, Action taken on the

Based on: STAT03_A Statistical Analysis Plan

Version 5.0, Effective Date 16-Dec-2016

Confidential and intellectual property of Assign DMB. No part of this document or its contents may be duplicated, referenced, published or otherwise disclosed in any form or by any means without prior written consent of Assign DMB.

Page 45 of 47

				investigational product, Outcome
	Х	Х	Serious AEs (Randomized subjects)	Subject number, Treatment group, AE term,
4.11				Part 1: Country, MedDRA Preferred Term,
				System organ class, Start date, End date,
				Medically attended
4.12				Part 2: Severity, Serious AE, Causality, Action
				taken in general, Action taken on the
				investigational product, Outcome
	х	х	AEs leading to death (Randomized subjects)	Subject number, Treatment group, AE term,
4.13				Part 1: MedDRA Preferred Term, System organ
				class, Start date, End date, Medically
				attended
4.14				Part 2: Severity, Serious AE, Causality, Action
				taken in general, Action taken on the
				investigational product, Outcome
4.15		х	Hematology laboratory parameter (Randomized	Subject ID, Country, Treatment group, Visit,
			subjects)	Date, Parameter, Value (site), Unit (site),
1				Normal range, Clinical relevance, Causal
				relationship, Value (standard), Unit (standard),
				Change from screening
4.16		х	Clinical chemistry laboratory parameter	Subject ID, Country, Treatment group, Visit,
			(Randomized subjects)	Date, Parameter, Value (site), Unit (site),
				Normal range, Clinical relevance, Causal
				relationship, Value (standard), Unit (standard),
				Change from screening
4.17		х	Coagulation laboratory parameter (Randomized	Subject ID, Country, Treatment group, Visit,
			subjects)	Date, Parameter, Value (site), Unit (site),
				Normal range, Clinical relevance, Causal
				relationship, Value (standard), Unit (standard),
			···· · · · · · · · · · · · · · · · · ·	Change from screening
4.18		х	Urinalysis (Randomized subjects)	Subject ID, Country, Treatment group, Visit,
				Date, Parameter, Value/Result, Unit, Normal
				range, Clinical relevance, Causal relationship,
1.10				Specification
4.19		х	Vital signs (Randomized subjects)	Subject number, Country, Treatment group,
				Visit, Date, Systolic blood pressure [mmHg],
				Diastolic blood pressure [mmHg], Pulse rate
1.00				[b/min], Body temperature [°C]
4.20		х	Symptom-directed physical exam (Randomized	Subject number, Country, Treatment group,
4.04	 		subjects)	visit, Symptom, Symptom present
4.21		х	Local tolerability (Randomized subjects)	Subject number, Country, Treatment group,
				Visit, Time-point, Date and time, Symptom,
4.00				Symptom present
4.22		Х	System-based assessment (Physical	Subject number, Country, Treatment group,
			examination, Randomized subjects)	VISIT, Assessment necessary, Body system,
				Result, Specification
4.23		х	Pregnancy test (Randomized subjects)	Subject number, Country, Treatment group,
				visit, Urine pregnancy test performed, Date of
	1	1		of pregnancy test, Result

Confidential and intellectual property of Assign DMB. No part of this document or its contents may be duplicated, referenced, published or otherwise disclosed in any form or by any means without prior written consent of Assign DMB.

